7.4.1 Study Treatments

Each participant will be followed for a duration of 24 months. Study visits will take place at the site from which each participant is enrolled. Routine clinical exams and blood work will be done as indicated for clinical care with results documented for the study, as appropriate. Participants will be randomly assigned 1:1 to one of two research groups. The Routine Group will have 7 study visits over 2 years at the clinic. The Extended Group will have 6 study visits over 2 years at the clinic.

- **ROUTINE GROUP:** The routine group will receive the HPV vaccine (GARDASIL®9) at the routine vaccine schedule of three doses given at month 0, month 2, and month 6.

- **EXTENDED GROUP:** The extended group will receive the HPV vaccine (GARDASIL®9) at an extended vaccine schedule of three doses given at month 0, month 6, and month 12.

7.4.2 Study Duration

The primary endpoint occurs at month 7 prior to completion of all doses in the extended interval group. All additional endpoints beyond month 7 are based on completion of the three doses and will provide critically-needed data on extended dosing intervals, HPV self-sampling acceptability, safety, and efficacy of 9vHPV vaccines in WLWH for whom the data is currently extremely limited. The 24-month follow-up duration will allow us to map immune titer dynamics to the vaccine out to the expected plateau in immunocompetent populations based on our prior data from WLWH (data not published) as well as the general population.^{34, 35}

7.4.3 Timing of Study Visits

Where possible, study visits will be scheduled on the same day as the participant's routine clinic visits for HIV care.

7.4.4 Delays and Contraindications to Study Procedures

7.4.4.1 Indications for a Delay in Vaccination

Vaccination may occur after the following condition has resolved and no other exclusion criteria are met.

- Current febrile illness or oral temperature over 38.5C
- Moderate to severe illness within 24 hours of study vaccine administration
- Vaccinations will be suspended in pregnant women and may resume following the resolution of the pregnancy
- Administration of immunoglobulins and/or any blood products within 30 days of a vaccination
- Any live virus vaccines given within 28 days of vaccination.
- Inactivated or recombinant vaccines (e. Influenza, Hep B, Tdap, Men C, COVID-19) may be given up to 8 days before a study HPV vaccination or at least 8 days following the study vaccine

Exceptions may be made under exceptional circumstances, for instance if a participant is from out of town and additional travel to the site for additional vaccination (eg. Influenza vaccine) would prove very difficult. In this case, document the additional vaccines clearly in the source documents and indicate the date given

7.4.4.2 Indications for a Delay in Vaginal Swab Sampling

- Self-obtained samples may continue to be collected during pregnancy.

- Participants must not be menstruating at the time of the vaginal swabbing. The participant may have all other study procedures performed. The participant will be invited to take the swabs home to self-collect when they are not menstruating with instructions on how to return the swabs to the study centre.

7.4.4.3 **Indications for a Delay in Study Blood Sampling**

- Administration of immunoglobulins and/or any blood products within 30 days of study blood sampling
- Administration of any live virus vaccines given with 28 days of a blood sample
- Administration of inactivated or recombinant vaccines (e.g. Influenza, Hep B, Tdap, COVID) up to 8 days before study blood sample collection is acceptable

7.4.4.4 **Contraindication for Continuation of Study Procedures**

- Withdrawal from the study
- Anaphylactic reaction to HPV vaccine related component
- Development of any newly confirmed or suspected immunosuppressive or immunodeficient condition (other than HIV/AIDS)
- Administration of any HPV vaccine not provided as part of the study
- Investigator decides it is not in participant's best interest
- Participant decides to discontinue vaccine series

7.4.5 **Outline of Study Visits**

Month 0

At the Month 0 visit, the following will be done:

- Collection of informed consent.
- Baseline information will be recorded including information such as: general health history, HIV history and medication history, current antiretroviral medications
- A brief physical assessment (temperature, height, weight).
- Regular clinic and study bloodwork.
- A urine pregnancy test (regardless of age or sexual activity).
- A short questionnaire regarding how the participant feels about self-collecting a vaginal swab for the purpose of HPV screening for cervical cancer.
- A self-collected vaginal swab for detection of HPV DNA, and a retention swab.
- The first of three HPV vaccine doses will be given.
- Instructions regarding the 14-Day Post-Vaccine Symptom Diary

Month 1

At the month 1 visit the following will be done:

- Assess ongoing consent.
- Review of any changes in health status and/or medications.
- Review of all adverse events occurring in the first 14 days following vaccination and any significant adverse events following this period.
- Study bloodwork.

Month 2

This visit will only occur in participants in the routine group.

At the month 2 visit, the following will be done:

- Assess ongoing consent.
- A brief assessment of vaccine contraindications (including temperature).
- A urine pregnancy test (regardless of age or sexual activity).
- Review of any changes in health status and/or medications.
- Review of any significant adverse events last study visit.
- The second of three HPV vaccine doses will be given.
- Instructions regarding the 14-Day Post-Vaccine Symptom Diary
- PLEASE NOTE: there will be no blood drawn at this visit.

4 weeks after the Month 2 visit, the study coordinator will contact the participant to review any adverse events occurring in the first 14 days following vaccination and any significant adverse events following this period. This will act as a safety follow-up, as participants will not be seen in-person again until Month 6.

Month 6

At the month 6 visit the following will be done:

- Assess ongoing consent.
- A brief assessment of vaccine contraindications (including temperature).
- A urine pregnancy test (for all participants regardless of age or sexual activity).
- Review of any changes in health status and/or medications.
- Review of any significant adverse events following this period.
- An HPV vaccine dose will be given (for the routine group, this will be the 3rd and final dose; for the extended group, this will be the 2nd dose).
- Instructions regarding the 14-Day Post-Vaccine Symptom Diary
- A self-collected vaginal swab for detection of HPV DNA, and a retention swab.
- PLEASE NOTE: there will be no blood drawn at this visit for the routine group; study bloodwork will be done for the extended group.

Month 7

At the month 7 visit the following will be done:

- Assess ongoing consent.
- Review of any changes in health status and/or medication.
- Review of all adverse events occurring in the first 14 days following vaccination and any significant adverse events following this period.
- Study bloodwork.

Month 12

At the month 12 visit, the following will be done in participants from the routine group:

- Assess ongoing consent.
- Review of any adverse events since last study visit.
- A brief physical assessment (weight).
- A review of any changes in health status and/or medications.
- A self-collected vaginal swab for detection of HPV DNA, and a retention swab.
- PLEASE NOTE: there will be no blood drawn at this visit.

At the month 12 visit, the following will be done in participants from the extended group:

- Assess ongoing consent.
- A brief physical assessment (weight).
- A urine pregnancy test (regardless of age or sexual activity).
- A brief assessment of vaccine contraindications (including temperature).
- Review of any changes in health status and/or medications.
- Review of any significant adverse events since vaccination.
- A self-collected vaginal swab for detection of HPV DNA, and a retention swab.
- The third of three HPV vaccine doses will be given.
- Instructions regarding the 14-Day Post-Vaccine Symptom Diary
- PLEASE NOTE: there will be no blood drawn at this visit.

4 weeks after the Month 12 visit, the study coordinator will contact the extended group to review any adverse events occurring in the first 14 days following vaccination and any significant adverse events following this period. This will be act as a safety follow-up, as participants will not be seen in-person again until Month 24.

Month 24

At the month 24 visit, the following will be done:

- Assess ongoing consent.
- Review of any significant adverse events since last study visit
- A review of any changes in health status and/or medication.
- A short questionnaire regarding how the participant feels about self-collecting a vaginal swab for the purpose of HPV screening for cervical cancer.
- A self-collected vaginal swab for detection of HPV DNA, and a retention swab.
- Study bloodwork.

5. Study Procedures in Detail

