7.2.1 Suspension of Study Procedures in Pregnancy

In the event of a pregnancy during the study, the investigative site is to notify [name] at the Study Coordinating Centre using a pregnancy reporting form as soon as the investigative site is made aware of the pregnancy. Following the resolution of the pregnancy, the investigative site will provide an update to the Pregnancy Reporting Form and inform the Study Coordinating Centre.

Study vaccination is to be suspended in pregnant participants and may be resumed at the resolution of pregnancy. All other study procedures may continue.

If a participant has a positive pregnancy test as part of the study visit, the clinic doctors or nurses will be notified and they will let the participant know about the result. If the participant receives a positive test outside of the clinic, they are asked to let the team know. Following the diagnosis of pregnancy, study vaccination will be temporarily stopped, and participants will be invited to resume vaccination at the same point that it was stopped, 1 month after the conclusion of the pregnancy if they choose to do so.

Pregnant participants will be invited to sign a Pregnancy Consent Form.

Information to be collected following signing of the Pregnancy Consent includes:

- estimated date of delivery
- the outcome and mode of delivery
- any important diagnoses associated with the pregnancy and delivery
- the date of birth or pregnancy loss
- the gestational weeks at birth or pregnancy loss
- infant's sex and weight
- infant's APGAR scores

- if the infant was required to stay in hospital longer than usual, and if so, what the cause was

3. Summary of Study Visits

Table 1A. Schedule of Visits (Routine Group: Follows Routine Vaccine Schedule)

	Informed Consent	Pregnancy Test	9vHPV Vaccine	Blood Draw	HPV DNA Swab ^a	AE Assessment	Ongoing Medical History	HPV Self-Sampling Questionnaire
Month 0	X	X	X	X ^c	X	X	X	X ^b
Month 1				X		X	X	
Month 2		X	X			X	X	
Month 6		X	X		X	X	X	
Month 7				X		X	X	
Month 12					X	X	X	
Month 24				X	X	X	X	X

^aSelf-sampling where acceptable to participant, ^b Pre-HPV-swabs, ^c Pre-vaccination

Table 1B. Schedule of Visits (Extended Group: Follows Extended Vaccine Schedule)

	Informed Consent	Pregnancy Test	9vHPV Vaccine	Blood Draw	HPV DNA Swab ^a	AE Assessment	Ongoing Medical History	HPV Self-Sampling Questionnaire
Month 0	X	X	X	X ^c	X	X	X	X ^b
Month 1				X		X	X	
Month 2								
Month 6		X	X	X ^c	X	X	X	
Month 7				X		X	X	
Month 12		X	X		X	X	X	

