10.0 PARTICIPANT RECRUITMENT AND WITHDRAWALS

1. Recruitment

We will recruit and enroll WLWH over a 36-month period starting in January 2023. Recruitment will be at our 10 sites of HIV and/or reproductive care, when WLWH attend for routine care, in collaboration with their healthcare providers. Due to the high frequency of standard clinical HIV care visits, we anticipate that all participants can be recruited during clinic attendance for routine visits.

2. Participant Compliance

In our precursor study of 4vHPV vaccination, 90% of WLWH completed the 3-dose vaccination schedule. As we are recruiting from sites of HIV/reproductive care, these women are generally engaged in care and accustomed to frequent clinical visits that include procedures such as blood draws. Engagement with WLWH confirms their desire to have

their clinical questions answered through appropriate research. Moreover, this vaccine is not publicly funded in all provinces for older women so trial participation provides enhanced access to vaccine.

3. **Rate of Loss to Follow Up**

In our sample size calculation, we have allowed for 10% loss to follow-up between enrolment and primary outcome (month 7 serology). This is conservative and based on 10% attrition/year in our precursor study.

4. **Withdrawals**

Investigators or their delegates will attempt to contact those study participants who do not return for study visits. Study personnel will make at least three attempts to contact the participant using various communication means. Each attempt should be documented in the participant source documents.

A participant completing all visits up to and including the Month 24 visit will be considered to have completed the study.

Withdrawals will not be replaced. All withdrawals will be documented including the date of the withdrawal and the reason.

11.0 **TRANSPORTATION OF LABORATORY SAMPLES**

All shipments of serum samples are to be shipped frozen and prepared by qualified individuals ensuring that all shipments are packed and shipped according to IATA regulations and are to be packed using dry ice.

All shipments of HPV DNA testing aliquots are to be shipped frozen and prepared by qualified individuals ensuring that all shipments are packed and shipped according to IATA regulations.

All samples are to be clearly labeled with participant's 5-digit PID#, date of collection, and visit month.

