Subgroup analyses by gender (woman, gender-diverse) will be conducted if sample size allows, examining differences in all outcomes by gender. Primary and secondary analyses will be analyzed by clinical and demographic variables including: age, ethnicity, region, CD4+ T cell count, HIV viral load suppression (vs. unsuppressed), and HPV DNA or anti-HPV antibody positivity at baseline.

7. **Sample Size Calculations**

The sample size was calculated based on the primary evaluation of non-inferiority of the immunologic response to 2 vs. 3 doses of 9vHPV vaccine. For ethical reasons, all 2 dose recipients will eventually receive a third dose but we used a dose ranging study design to achieve this end. Using a one-sided alpha = 0.025, a non-inferiority margin of 0.5 based on benchmarks set by Merck for other immunobridging studies leading to licensure,⁴³ a standard deviation of 1.379 calculated from HPV16 GMTs in our prior cohort of WLWH, and 80% power, we would require 205 participants per group (total: 410). Given an anticipated dose completion rate of 90% based on our prior experience, we aim to recruit 225 participants per group to achieve power to detect non-inferiority in peak 2 vs. 3 dose GMT.

At 6 of our 10 sites, there are >900 WLWH who are unvaccinated and eligible for this study, suggesting there are likely ~1800 eligible women at all sites. We therefore anticipate being able to achieve the target sample size of 450 given that 90% of eligible WLWH screened in our precursor study were enrolled.

14.0 **DATA MANAGEMENT**

The data safety and monitoring committee (DSMC) will be coordinated through established processes by the CTN and will function at pre-specified intervals to monitor the conduct and progress of the trial, evaluate the accumulating study data including all serious adverse events, recommend protocol changes, alert trial leaders to emerging procedural or ethical issues, and monitor enrolment to ensure timely conduct of the trial. All up to date adverse events will be reported to the DSMC at each meeting to ensure participant safety. All other data including immunogenicity, efficacy, and self-sampling acceptability will be reported to the DSMC as it becomes available throughout the study for assessment of study conduct and progress. Reports from the data management process will be provided to the DSMC to ensure data quality.

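### Read literally, Protocol 7.4.4.4 stops scheduled blood and swabs as well as further doses after immune or vaccine-related triggers; a doses-only intent is possible but is not stated

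*Protocol*

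**What the plan says.** Section 7.4.4 deals with study procedures one kind at a time: vaccination in 7.4.4.1, vaginal swabs in 7.4.4.2 and study blood in 7.4.4.3. Section 7.4.4.4 then gives six contraindications to continuing study procedures, without naming a kind. One is "Development of any newly confirmed or suspected immunosuppressive or immunodeficient condition (other than HIV/AIDS"); another is "Participant decides to discontinue vaccine series". The other four are withdrawal from the study, anaphylaxis to a vaccine component, an HPV vaccine from outside the study, and the investigator's judgement of the participant's interest. The list has no time limit.

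For pregnancy, 7.2.1 suspends vaccination and adds: "All other study procedures may continue". Section 7.4.4.2 also lets swabs continue in pregnancy. No such sentence accompanies 7.4.4.4.

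Three other places bear on the consequences. Section 7.4.2 states: "All additional endpoints beyond month 7 are based on completion of the three doses". Section 13.7 sets enrolment with the words "Given an anticipated dose completion rate of 90% based on our prior experience". Section 7.4.1 gives the extended group "an extended vaccine schedule of three doses given at month 0, month 6, and month 12", while routine dosing ends at month 6.

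**The concern.** A rule that stops dosing is a safety rule. A rule that stops outcome collection creates missing data, and here the missing data would follow events after randomisation that are plausibly related to titre or HPV persistence. Because there is no time limit, the literal rule also reaches a fully dosed woman who is waiting only for her month-24 visit, and for her a suspected immune condition would be enough.

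At stake are the month-24 blood and swab, the month-12 swab and, for early triggers, the month-7 blood. Analysis cannot recover a sample that was never taken. The mixed-effects model in 13.4 would still use these women's earlier titres. But neither it nor the imputation in 13.1 would have a sample taken after the event to learn from. Sites may also read the section differently, so follow-up could vary by site.

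**Working it through.** **Text check**

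1. *Do study procedures include sampling?* Section 7.4.4 covers vaccination, swabs and blood under that one term. Section 7.4.4.2 lets a menstruating woman have all the other study procedures, which makes the swab one of them. The part that details study procedures (7.5) includes blood work (7.5.5) and swabs (7.5.8). So the literal scope of 7.4.4.4 includes sampling.
2. *Is stopping the series the same as leaving the study?* No. Withdrawal from the study is a separate bullet.
3. *Does any other section keep sampling going?* Section 7.4.1 says in general terms that participants are followed for 24 months, 9.2.3 follows SAEs, and 10.4 covers contact attempts and withdrawals. None mentions blood or swabs after a 7.4.4.4 event.
4. *What is not lost?* SAE recording (9.2), updates on new illnesses (9.1) and registry linkage or chart review (7.5.11) do not depend on this section. The gap concerns blood and swabs.

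**Illustrative size**

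The protocol states no figure for these triggers, so there is none to reproduce. Its usable inputs are 450 women (5.1), 90% completion (13.7; 10.2 reports "90% of WLWH completed the 3-dose vaccination schedule"), 10% attrition a year (10.3: "This is conservative and based on 10% attrition/year in our precursor study") and SD 1.379 (13.7). I take the SD as natural-log, which the protocol does not state. Everything else below is assumed.

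*New immune condition.* Assume that p = 1% to 5% of women are affected, with onset uniform over 24 months and a full titre drop of d = 2 to 4-fold, half of it on the log scale on average.
- Expected at month 24: 450 × 0.9² = 364.5. Affected: 3.6 to 18.2, about 4 to 18 women.
- Before the month-7 blood: 450 × 0.9 × 7/24 × p = 1.2 to 5.9, about 1 to 6 women.
- Complete-case overstatement of the overall month-24 GMT: d^(p/2) − 1 = 2^0.005 − 1 = 0.35% to 4^0.025 − 1 = 3.5%.
- For comparison, the 95% CI factor is exp(1.96 × 1.379/√364.5) = 1.15.
- Between-arm ratio: no shift if the arms are affected equally.

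*Stopping the series.* 10% of 450 is 45 non-completers. Assume that a share s = 10% to 50% would still attend: 4.5 to 22.5, about 5 to 23 women.
- If stopping follows the number of doses offered (two after baseline in each arm), month-24 removal is equal and the ratio does not shift.
- If stopping follows time, it reaches 10% by month 6 in the routine arm and 1 − 0.9² = 19% by month 12 in the extended arm. Removal differs by 9 points × s = 0.9 to 4.5 points, or 2 to 10 of 225 women.
- With 2-fold lower titres in the removed women, the ratio shifts by 2^0.009 = 1.006 to 2^0.045 = 1.032, raising the extended arm.
- Between-arm SE: 1.379 × √(2/182.25) = 0.144. The shift is 0.04 to 0.22 SE.

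*Month 7.* Time-based stopping gives 10% by month 6 in both arms, hence no shift. Dose-based stopping split evenly gives 10% routine against 5% extended by then. The difference is 5 points × s = 0.5 to 2.5 points. With 2-fold lower titres the largest shift is 2^0.025 = 1.017. Against an SE of 1.379 × √(2/202.5) = 0.137, that is 0.13 SE. It would raise the routine arm and so work against non-inferiority.

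**The case against.** The strongest reply is that the authors meant doses only. Three of the six bullets concern the vaccine itself: anaphylaxis, a non-study HPV vaccine and stopping the series. The heading of 7.2.1 uses the same term for a stop to vaccination alone. The general 24-month follow-up in 7.4.1 and the illness updates in 9.1 fit a woman who stays in the study. This stands as a credible reading, so the point is an ambiguity with a literal meaning that does harm, not a proven intention to stop sampling. But 7.2.1 needed a sentence to limit its scope, and 7.4.4.4 has none.

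A second reply is that 7.4.2 ties endpoints after month 7 to three doses, so not sampling women who stop the series is consistent with the plan. That could justify leaving them out of an analysis. It is a weak reason not to take the samples, and it does not cover a fully dosed woman with a new condition.

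A third reply is that the numbers are soft. That is correct. The 45 non-completers overlap with loss to follow-up, because the same 10% appears as attrition in 10.3 and as dose non-completion in 13.7. The 19% is not a protocol figure. The GMT calculation ignores the earlier titres that the mixed-effects model would use.

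A reader might also argue that women who decline dose 3 at month 12 are needed to show two-dose persistence. The protocol sets no such objective: the month-24 objective in section 3.0 compares the two schedules.

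**Conclusion.** The point holds as a minor, inexpensive improvement. Read literally, 7.4.4.4 ends scheduled blood and swabs after immune or vaccine-related triggers, and nothing in the protocol limits it to doses. It could lose month-24 samples, and some month-7 samples, from women whose titres may differ.

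The likely effect on between-arm results is small and cannot be quantified from the protocol. The illustrative shifts reach 0.22 SE at month 24 and 0.13 SE at month 7. They rest on assumed incidence, titre drop, willingness to attend, timing of stopping and the log scale of the SD.

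A reader might infer that the trial will be materially biased or that the month-7 non-inferiority result is at risk. The documents do not support that. There is no evident reason for a new immune condition to differ by arm, and only series discontinuation has a mechanism for a difference, because the dosing calendars differ. Nor do they support the inference that safety follow-up ends.

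**What to change.** Amend 7.4.4.4 so that four triggers end further study vaccine doses only: a new immunosuppressive condition, anaphylaxis, a non-study HPV vaccine, and a decision to stop the series. After a new immunosuppressive condition, further dosing is at the investigator's discretion. Then state, as 7.2.1 does for pregnancy, that scheduled blood, swabs and safety follow-up continue to month 24 unless the participant withdraws consent or the investigator judges continuing not to be in her interest.

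Leave the analysis set to the SAP. How these women enter the mITT analysis, and the month-24 analyses that 7.4.2 ties to three doses, is an analysis decision. The protocol's task is to secure the samples.

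The cost is a few sentences in an amendment, with no new visits or procedures. The downside is slightly more heterogeneous titres. If doses only was always the intent, the amendment simply makes it explicit.

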9.0 ADVERSE EVENTS AND SERIOUS ADVERSE EVENTS

Please ensure that a comprehensive medical history is taken and documented prior to vaccination to ensure that only new adverse events are captured as AEs.

1. Adverse Events

All adverse events will be collected during the vaccination phase of the study for up to 14 days following a vaccine. Documentation should include, diagnosis (or symptom if not diagnosed), start and stop dates, intensity (using the DAIDS AE grading table), and treatments. Narrative notes should detail the event and possible contributing factors. All AEs collected in the vaccination phase of the study (up to 14 days following a vaccine) must be assessed as to their relationship to the vaccine and signed off by a site investigator.

All newly diagnosed chronic illnesses; worsening, increase in severity, or frequency of pre-existing conditions; or medically significant illnesses occurring more than 14 days after the administration of the vaccine will be collected throughout the entire study as updates to the general medical history.

2. Serious Adverse Events

Serious adverse events (AEs), medically attended AEs, and provincially reportable AEs following immunization will be collected. Serious AEs will be defined per GCP-ICH guidance and all will be collected regardless of presumed relatedness and/or expectedness. AEs will be reviewed at each study visit, and participants will have emergency contact details for the local research team to report events between visits.

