1. To determine if 2 doses of 9vHPV vaccine are non-inferior to 3 doses in WLWH for the additional 9vHPV types not in the primary outcome, we will evaluate serologic response by comparing peak anti- HPV6/11/31/33/45/52/58 GMTs individually and seroconversion rates with 95% CI at 7 months in both groups using linear and logistic regression, respectively, adjusted for HIV viral load, CD4+ T cell count, and age.
2. As the world is moving towards one-dose HPV vaccine schedules, we will take the opportunity to collect preliminary data on the peak one-dose antibody response at month 1. These data will inform the sample size calculation for a future one-dose trial, as appropriate, and will be reported as anti-HPV16/18 GMTs with 95% CI.
3. To evaluate significant adverse events, the proportion (and 95%CI) of participants who experience significant adverse events will be calculated for the entire study population, and also by group. The types and severities of adverse events will be described.
4. To address vaccine efficacy, we will calculate incidence rates of abnormal cervical cytology and histology (HSIL), and breakthrough persistent HPV infection. HSIL will be described with Kaplan-Meier curves. If sufficient numbers of each are observed, Kaplan-Meier curves will be calculated by age range (21-30, 31-39, 40-55, >55), CD4 count (<200, 200-500, >500), HIV viral load (detectable vs. undetectable), and prior HPV status. Persistent HPV will be described by type of HPV, high vs. low-risk, and vaccine type or not, using Kaplan-Meier curves for HPV acquisition and frequencies and percentage for persistent infections. Given the capability to intervene with early pre-cancerous changes in the cervix, we cannot ethically use cervical cancer as an end point but other efficacy endpoints are critical for an HPV vaccine study as an immune correlate of protection is unknown.
5. To assess the uptake of HPV vaccination of WLWH, a screening log will be kept by each study site to track how many WLWH aged 18-45 were not eligible to participate in the study due to having already received an HPV vaccine. The proportion of women who were previously vaccinated will be calculated for the population of women aged 18-45 at each site and across the country.

6. **Planned Subgroup Analyses**

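### At month 12 the adverse-event question differs between the randomised arms in breadth and look-back, and the routine-arm version conflicts with section 9.1

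*Protocol*

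**What the plan says.** The month 12 lists in section 7.4.5 are written separately by arm. The routine list has "Review of any adverse events since last study visit". The extended list has "Review of any significant adverse events since vaccination".

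By then the routine arm has completed its series. The month 6 list says that "for the routine group, this will be the 3rd and final dose", and the month 7 list, common to both arms, calls for "Review of all adverse events occurring in the first 14 days following vaccination and any significant adverse events following this period". The extended arm receives its third dose at month 12, and four weeks later "the study coordinator will contact the extended group to review any adverse events occurring in the first 14 days following vaccination", followed by any significant events after that.

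Section 9.1 sets one rule without regard to arm: "All adverse events will be collected during the vaccination phase of the study for up to 14 days following a vaccine". After that window only new chronic illness, worsening of existing conditions and medically significant illness are taken, as medical-history updates: "medically significant illnesses occurring more than 14 days after the administration of the vaccine will be collected throughout the entire study". Section 9.2 adds serious, medically attended and provincially reportable events, and section 9.2.1 records serious events at any time.

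For analysis, section 13.5 item 3 plans the proportion of participants with significant adverse events. These proportions "will be calculated for the entire study population, and also by group. The types and severities of adverse events will be described".

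**The concern.** Two randomised arms should be asked the same safety question over the same period. Here the breadth (any against significant) and the starting point (last visit against last vaccination) both change with allocation, and no reason is given. Participants and field staff know the allocation (section 5.2), so blinding offers no protection against a difference written into the visit list.

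Exploratory objective 6 is to describe the incidence, type and severity of adverse events. If sites follow the visit list literally, the routine arm contributes minor, late, post-vaccination events for which the extended arm has no matching question. A reader of the resulting description could take a difference in questioning for a difference between schedules. Section 14.0 also sends all adverse events to the safety committee, which would see the same imbalance.

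**Working it through.** No figure in the protocol bears on this point, so the check compares texts. The adverse-event questions in section 7.4.5 are:

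| Contact | Routine arm | Extended arm |
|---|---|---|
| Month 1 | all in first 14 days, then significant | same |
| Month 2 | significant | no visit |
| 4 weeks after month 2 | any in first 14 days, then significant | no contact |
| Month 6 | significant | significant |
| Month 7 | all in first 14 days, then significant | same |
| Month 12 | **any**, since last visit | **significant**, since vaccination |
| 4 weeks after month 12 | no contact | any in first 14 days, then significant |
| Month 24 | significant | significant |

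1. **Post-dose windows are balanced.** Routine doses at months 0, 2 and 6 are covered by month 1, the contact after month 2, and month 7. Extended doses at months 0, 6 and 12 are covered by month 1, month 7, and the contact after month 12. Each arm has 3 × 14 = 42 days of all-event review.

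2. **The routine month 12 line is the outlier.** Every other review outside the 14-day window is limited to significant events.

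3. **Look-back.** The routine arm's last visit is month 7, so its window is 12 − 7 = 5 months. The extended arm's last dose before the visit is at month 6, so on the natural reading its window is 12 − 6 = 6 months. Its first month was already reviewed at month 7.

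4. **Conflict with 9.1.** For a participant on schedule, the routine arm's 5-month window opens about a month after the last dose and contains no 14-day post-dose period. Section 9.1 does not call for non-significant events there, yet the visit list asks for them. A site cannot follow both.

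5. **Reach into the analysis.** The statistic planned by group counts participants with *significant* events. *Any* includes *significant*, so both month 12 questions capture what that statistic needs. The next sentence of item 3, on types and severities, is limited neither to significant events nor to a time window, and it is not stated to be by group. The extra routine-arm events can enter there. A second route is classification: the protocol uses the term significant adverse event repeatedly but defines only serious events, so wider questioning in one arm may yield more events that are then called significant.

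**The case against.** The strongest reply is that this is a drafting slip with little effect. The month 2 and month 6 bullets are loosely worded too. The objective is exploratory and descriptive, and names no comparison of arms. Section 9.1 already directs late events to the medical history, so a site that follows it would not record a minor illness at month 9 as an adverse event. The extended arm is not left unquestioned either. Its month 12 list includes a review of changes in health status and medications, Tables 1A and 1B mark the adverse-event assessment at month 12 alike, and section 9.2 collects serious and medically attended events in both arms.

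Much of this stands, and it limits the point. A reader might infer that the planned by-group safety comparison is itself biased. The documents do not support that, because the statistic is confined to significant events and both arms are asked for those. A reader might also wish to put a count on the surplus routine-arm events. The protocol gives no background event rate, so any count would rest on an assumed rate and on sites overriding 9.1.

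The reply does not remove the contradiction. The visit list and 9.1 give sites different instructions in one arm only, and nothing says which prevails.

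**Conclusion.** The point holds as a minor inconsistency. At month 12 the adverse-event question differs by arm in breadth and look-back, and the routine-arm line conflicts with section 9.1. What is collected can therefore differ by arm over months 7 to 12. This can reach the description of types and severities if that description is shown by arm and includes events later than 14 days after a dose. It can also reach the significant-event proportion indirectly, through an undefined term.

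No size is given because none follows from the document. The conclusion assumes that participants are on schedule, that sites work from the visit list at least in part, and that *since vaccination* in the extended list means since the month 6 dose.

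**What to change.** Use the same line for both arms at month 12: significant adverse events since the last study visit. Keep the existing contact four weeks after the extended arm's third dose. Reconcile the line with sections 9.1 and 9.2, including what counts as significant.

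Limit any by-arm adverse-event summary to events collected the same way in both arms: all events within 14 days of each dose, plus significant, serious and medically attended events at any time. A tempting shortcut is to count non-serious events only within 14 days of a dose. That should be avoided, since it would drop later significant and medically attended non-serious events that sections 9.2 and 13.5 provide for.

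The cost is one line in the visit outline, the matching source template and case report form, and a sentence on the summary. The only data given up are minor late routine-arm events that 9.1 does not call for. Where month 12 visits have already taken place, the summary rule deals with the events already recorded.
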